ASSESSMENT SCHEDULE	
Visit schedule: On-site visits every 12 weeks throughout the study, for a maximum of 12 post baseline visits. The Start-of-treatment (Visit 1) may be performed on the same day as the TRAVERSE-LTS12551 EOT Visit.
 
Early termination: Patients who prematurely and permanently discontinue IMP administration should have the EOT/EOS Visit (Visit 13) performed. Women of child-bearing potential discontinuing treatment will be advised to avoid pregnancy for at least 12 weeks following the last IMP dose.

STATISTICAL CONSIDERATIONS	
Sample size determination: Qualifying patients completing the treatment period of study TRAVERSE-LTS12551 will be offered to continue in this study.
 
Primary analysis population: Safety: All patients receiving at least one dose of study medication during this study.
 
Primary/key analysis: All TEAEs, AESIs, SAEs, and AEs leading to treatment discontinuation will be summarized.

DURATION OF STUDY PERIOD (per patient)	Until dupilumab approval for use in asthma and market availability to the patient, or for a maximum of 144 weeks (ie, about 3 years) after the Start-of-treatment (Visit 1), whichever comes first.

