9.2 SECONDARY ENDPOINTS

- Incidence rates and event rates per 100 patient-years for AESIs over the study.
- Incidence rates for SAEs/death over the study.
- Incidence rates for AEs leading to study discontinuation over the study.

Note: AEs, SAEs, AESIs, AEs leading to IMP discontinuation, and death will be collected from the time of informed consent signature and then at each visit until the EOT/EOS (Visit 13). The safety analysis will be based on the reported AEs and clinical laboratory data. The study specific and general safety criteria are detailed in [Section 10.4.1](#).

Adverse events, AESIs, SAEs, AEs leading to IMP discontinuation and deaths will be reported as described in [Section 10.4.2](#) and analyzed as in [Section 11.4.3.1](#).

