10.1.5 End-of-study Visit

Patients who prematurely and/or permanently discontinue treatment will be scheduled for the EOT Visit, and the EOS Visit will be scheduled for 12 weeks later for follow-up on AEs.

The following procedure will be performed during this visit:

- Inquire for any AEs. In case of any such occurrences, AEs should be recorded and reported.

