11.4.3.1.1 Treatment-emergent adverse events

Incidence of TEAE and the number of TEAEs per 100 patient-years (total number of events adjusted for the total duration of exposure) will be presented by system organ class (SOC), high level group term (HLGT), and preferred term (PT) sorted in alphabetical order, the number and percentage (%) of patients experiencing a TEAE.

In the derivation of incidence of AEs, multiple occurrences of the same event in the same patient will be counted only once in the tables. The denominator will be based on the total number of patients in the safety population.

The proportion of patients with at least one TEAE, serious TEAE, and TEAE leading to discontinuation of the study will be tabulated. In addition TEAEs will be described according to maximum intensity and relationship to the study drug.

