11.4.3.1.2 Adverse events

An overview summary will be presented of the number (%) of patients with:

- Any TEAE.
- Any SAE and AEs leading to death (regardless of treatment-emergent status).
- Any treatment-emergent SAEs.
- Any AE leading to permanent study discontinuation.

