1.4 STUDY PLAN

The LPS15023 study consists of 3 periods:

- Start-of-treatment Visit (Visit 1): After completing the EOT Visit (Visit 17) in TRAVERSE, eligible patients should rollover into LPS15023.
- Treatment period (Visit 2 to Visit 12): Open-label treatment for up to 144 weeks (Visit 13, approximately 3 years).
- End-of-treatment/End-of-study (Visit 13).

Patients who prematurely and/or permanently discontinue treatment will be scheduled for the EOT Visit, and the EOS Visit will be scheduled for 12 weeks later for follow-up on AEs.

Statistical Analysis Plan
LPS15023 - Dupilumab

15-Mar-2021
Version number: 2.0

After completing the treatment period in TRAVERSE, eligible patients who have signed the informed consent form (ICF) should perform the assessments of the Start-of-treatment Visit (Visit 1). Patients will receive treatment until dupilumab approval for use in asthma and market availability to patients, or for a maximum of 144 weeks (i.e. about 3 years) after the Start of treatment (Visit 1), whichever comes first.

The end of clinical trial is defined as the “last patient last visit” planned in the protocol, i.e. the EOT/EOS Visit (Visit 13). The Sponsor reserves the right to discontinue the study at any time.

Study Flow Chart (copied from [section 1.1](#) of protocol)

Study periods	Start-of-Treatment	Treatment Period (144 weeks)	End-of-Treatment / End-of-Study
Week (W)	W0	W12-W132 (Visit every 12 weeks)	W144
VISIT	V1 ^a	V2-V12 ^b	V13 ^c
Enrollment			
Informed consent	X		
Patient demography	X		
Eligibility criteria	X		
Treatment			
Contact IRT	X	X	X
IMP dispensation/administration ^d	X	X	
IMP accountability	X	X	X
Injection training/technique observation ^e	X	X	
Dispense home-dosing diary ^f	X	X	
Safety			
Clinical laboratory ^g	X ^h	X	X
Adverse event reporting	X	X	X
Symptom-driven physical examination and vital signs	X	X	X
Concomitant medications	X	X	X

AE = adverse events; eCRF = electronic case report form; EOS = end-of-study; EOT = end-of-treatment; IMP = investigational medicinal product; IRT = interactive response technology; q2w = every 2 weeks; V = (study) visit; W = (study) week; WOCBP = women of child-bearing potential.

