2.3.2 Safety population

The primary analysis population is the safety population, defined as all patients who have received at least one dose or part of a dose of dupilumab during this study.

Statistical Analysis Plan
LPS15023 - Dupilumab

15-Mar-2021
Version number: 2.0

The treatment-emergent period is defined as the time from the first dose of dupilumab up to the last dose of dupilumab plus 2 weeks for completers, or plus 12 weeks for prematurely discontinued subjects.

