2.4.5.1 Analyses of adverse events

Analysis of Primary Safety Endpoint

Incidence rates of TEAEs with corresponding 95% CI (by the Clopper-Pearson method) will be calculated as follows:

- Incidence Rate (IR) = number patients with one or more TEAEs / number of subjects at risk (i.e. safety population) × 100

Event rates per 100 person-years of TEAEs with corresponding 95% CI (two-sided exact Poisson CIs) will be calculated. All events reported during the study follow-up period will be counted, regardless of whether they are reported in the same subject (i.e., multiple events per subjects), or different subjects. The person-years at follow-up will be calculated using the standard on-treatment duration formula: (the date of last IMP – date of first dose of IMP + 14 days)/365.25. Note that date of first dose of IMP, is in regards to first dose of this study, not first dose of the parent study. Event rate per person-years will be calculated as follows:

- Event rate (ER) = number of TEAEs / number of person-years at follow up

Analysis of Secondary Safety Endpoints

Incidence rates with corresponding 95% CI (Clopper-Pearson method) and event rates with corresponding 95% CI (exact Poisson method) will be presented for AESIs, described in [section 2.1.4.1](#), using the same methodology described above.

Incidence rates with corresponding 95% CI (Clopper-Pearson method) will be presented for SAEs/death over the study.

Incidence rates with corresponding 95% CI (Clopper-Pearson method) will be presented for AEs leading to study discontinuation over the study.

Generalities

The primary focus of adverse event reporting will be on treatment-emergent adverse events.

Statistical Analysis Plan
LPS15023 - Dupilumab

15-Mar-2021
Version number: 2.0

If an adverse event date/time of onset (occurrence, worsening, or becoming serious) is incomplete, an imputation algorithm will be used to classify the adverse event as pretreatment, treatment-emergent, or posttreatment. The algorithm for imputing date/time of onset will be conservative and will classify an adverse event as treatment emergent unless there is definitive information to determine it is pretreatment or posttreatment. Details on classification of adverse events with missing or partial onset dates are provided in [Section 2.5.3](#).

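### Treatment length varies by design, but SAEs/death and AEs leading to study discontinuation get a percentage with a Clopper-Pearson CI and no rate per 100 person-years; separately, the exposure categories labelled days fit only weeks (both minor)

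*SAP*

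**What the plan says.** **Duration.** The protocol summary sets the study period per patient as: "Until dupilumab approval for use in asthma and market availability to the patient, or for a maximum of 144 weeks", whichever comes first. SAP 1.4 repeats the rule: "Patients will receive treatment until dupilumab approval for use in asthma and market availability to patients, or for a maximum of 144 weeks". A patient who stops treatment prematurely has an EOT visit, and "the EOS Visit will be scheduled for 12 weeks later for follow-up on AEs" (Protocol 10.1.5).

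**Endpoints with a person-time rate.** SAP 2.4.5.1 gives TEAEs and AESIs a percentage with a Clopper-Pearson 95% CI and an event rate per 100 person-years with an exact Poisson 95% CI. Protocol 11.4.3.1.1 also plans, by SOC, HLGT and PT, "the number of TEAEs per 100 patient-years (total number of events adjusted for the total duration of exposure").

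**Endpoints without one.** For SAEs and deaths, SAP 2.4.5.1 says: "Incidence rates with corresponding 95% CI (Clopper-Pearson method) will be presented for SAEs/death over the study". The next sentence does the same for AEs leading to study discontinuation. Protocol 9.2 defines both endpoints this way, for example: "Incidence rates for AEs leading to study discontinuation over the study". The SAE and treatment-discontinuation tables in SAP 2.4.5.1 and the death summaries in SAP 2.4.5.2 give numbers and percentages only.

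**Event window.** SAP 2.3.2 runs the treatment-emergent period "up to the last dose of dupilumab plus 2 weeks for completers, or plus 12 weeks for prematurely discontinued subjects". The person-time formula in SAP 2.4.5.1 adds 14 days after the last dose for every patient.

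**Exposure table.** SAP 2.4.3.1 defines exposure as last dose date minus first dose date plus 14 days. It then lists nine categories, from `>0-4` to `>142`, and gives their unit as days.

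**The concern.** A percentage of patients with an event rises with the time they are watched. Here that time depends partly on when the product reaches the market for each patient, which has nothing to do with risk. The same underlying rate can therefore give quite different percentages. The Clopper-Pearson interval expresses sampling error around the percentage and does not adjust for length of follow-up. A reader who sets the SAE percentage beside another study, or beside an interim cut of this one, could take a difference in follow-up for a difference in risk. The plan guards against this for TEAEs and AESIs by adding a rate, but not for SAEs as a class, deaths or AEs leading to study discontinuation. In a study meant to describe long-term safety and late-onset events, those are results that readers will look up.

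The exposure table matters for the same reason, because it is where a reader would see how follow-up was spread. If programmed with the unit as labelled, it would show almost nothing about that spread.

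**Working it through.** The documents give no SAE rate, no exit dates and no precision target, so there is no planned figure to reproduce. The 750 is an expected enrolment. Part A is an illustration on assumptions; part B uses only the documents.

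**A. Percentage against rate**

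Inputs: N = 750 (Protocol 11.1, all taken as treated); maximum treatment 144 weeks. Assumed: a constant first-event hazard h, and follow-up equal to treatment exposure.

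Time in years: 24 weeks = 168/365.25 = 0.46; 48 weeks = 336/365.25 = 0.92; 144 weeks = 1008/365.25 = 2.76.

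*Step 1: everyone followed for the same time.* Percentage = 1 − exp(−h × T).

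| Assumed h per 100 PY | 48 weeks | 144 weeks |
|---|---|---|
| 3 | 2.7% | 7.9% |
| 5 | 4.5% | 12.9% |
| 10 | 8.8% | 24.1% |

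*Step 2: a fraction f leaves at Week 24 and the rest at Week 144, with h = 5 per 100 PY.*

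- Percentage = f(1 − exp(−0.05 × 0.46)) + (1 − f)(1 − exp(−0.05 × 2.76)).
- Person-years at risk, stopping at first event = 750 × percentage / 0.05.
- Total exposure = 750 × (f × 0.46 + (1 − f) × 2.76).

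| | f = 20% | f = 50% | f = 80% |
|---|---|---|---|
| Patients with an event | 81 | 57 | 33 |
| Planned percentage | 10.8% | 7.6% | 4.4% |
| Clopper-Pearson 95% CI | 8.7 to 13.2 | 5.8 to 9.7 | 3.0 to 6.1 |
| Person-years at risk | 1615 | 1137 | 659 |
| First-event rate per 100 PY (exact Poisson CI) | 5.0 (4.0 to 6.2) | 5.0 (3.8 to 6.5) | 5.0 (3.4 to 7.0) |
| Total exposure, PY | 1725 | 1207 | 690 |
| Crude rate from count and exposure (exact Poisson CI) | 4.70 (3.73 to 5.84) | 4.72 (3.58 to 6.12) | 4.78 (3.29 to 6.72) |

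The planned intervals at f = 20% and f = 80% do not overlap, although the hazard is the same. The first-event rate recovers it each time. The crude rate, which a reader could build from the patient count and mean exposure, comes close in both estimate and interval.

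*Step 3: which person-time to use.* A premature stop with 168 days of exposure has its last dose on day 154. Events count to day 154 + 84 = 238, but the SAP 2.4.5.1 person-time stops at day 154 + 14 = 168. The event window is 238/168 = 1.42 times as long. A new rate should therefore use person-time that covers the window in which its events are counted.

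**B. Exposure categories**

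- Minimum exposure, one dose: 0 + 14 = 14 days. Read as days, `>0-4` and `>4-12` can never be filled.
- Full treatment, last dose at Week 142: 142 × 7 + 14 = 1008 days = 144 weeks.
- The last cut point read as days: 142/7 = 20.3 weeks. Anyone treated to Week 24 (168 days) is already in `>142`.
- With dosing every 14 days there are 72 possible exposure lengths (14, 28, …, 1008 days). Read as days, 62 of them fall in `>142`. Read as weeks, they spread over all nine categories (2, 4, 6, 12, 12, 12, 12, 11, 1), and full treatment falls in `>142`.

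**The case against.** The study is single-arm and descriptive, and protocol and SAP agree on these endpoints. No planned comparison is distorted, and a percentage with an exact CI beside a report of exposure is a valid summary. All of that stands, and it is why the rate is offered as an improvement and not as a correction.

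Some of the gap is already covered. Serious infections, and anaphylactic or acute allergic reactions needing immediate treatment, are AESIs, so they receive a rate and a Poisson CI. Protocol 11.4.3.1.1 plans TEAE rates by SOC, HLGT and PT, though not by seriousness. The crude rate needs only the patient count and mean exposure, and so does its interval. That stands too: it would be wrong to say that the CI is lost. What remains is that no rate is reported for SAEs as a class, for deaths or for AEs leading to study discontinuation, so each reader must construct one.

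Three stronger readings are tempting, and the documents support none of them. A reader might infer that these endpoints have no confidence interval; the SAP specifies a Clopper-Pearson 95% CI for each percentage, and only the CI of an unplanned rate is absent. A reader might infer that the SAP departs from the protocol; it follows the endpoints in Protocol 9.2. A reader might infer that a planned result is invalid; none is.

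A fair criticism of the remedy is that a first-event rate differs in numerator and denominator from the all-events rates beside it. That is answered by labelling. The SAP also does not define completers, but this affects the TEAE window in general and is a separate matter.

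**Conclusion.** Minor, in two independent parts.

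1. The missing rate is a real but small gap. Under the assumed constant 5 per 100 person-years and 750 treated, the reported percentage moves from 4.5% at 48 weeks to 12.9% at 144 weeks, and from 10.8% to 4.4% as the share leaving at Week 24 goes from 20% to 80%. The hazards and exit patterns are assumptions; the direction of the effect does not depend on them. If the hazard differs between early and late leavers, a first-event rate also depends on follow-up, so it improves on the percentage without being free of the problem.

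2. The exposure unit is wrong as written. This rests on the SAP's own formula and the 144-week schedule. The consequence is confined to the categorical table, because the mean, SD, median and range of exposure are still reported.

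**What to change.** **1. SAP 2.4.5.1.** Keep the percentages and their Clopper-Pearson CIs. For treatment-emergent SAEs, deaths and AEs leading to study discontinuation, add the number of patients with an event per 100 person-years, with an exact Poisson 95% CI.

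- Take person-time from the first dose in this study to the first event, using AE onset as the event date. Without an event, run it to the end of the window in which events are counted: last dose plus 14 days for completers, plus 84 days for premature discontinuers (SAP 2.3.2 and 2.4.5). Classify patients as for TEAEs.
- Label it as a rate of patients with an event, distinct from the all-events TEAE and AESI rates.
- Label it as treatment-emergent. The protocol overview also counts "Any SAE and AEs leading to death (regardless of treatment-emergent status"), so the number behind the rate can be smaller than the count over the study.
- Record the addition in SAP 1.5 and 1.6.

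The cost is a few table lines and one extra derivation from dates already collected. The drawback is a second type of rate in the report.

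**2. SAP 2.4.3.1.** Change the unit of the exposure categories from days to weeks and record it in SAP 1.6. The cost is one word.

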10.3.2 Permanent treatment discontinuation with investigational medicinal product

Permanent treatment discontinuation is any treatment discontinuation associated with the definitive decision from the Investigator not to re-expose the patient to the IMP at any time during the study, or from the patient not to be re-exposed to the IMP whatever the reason.

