Adverse event incidence tables will present by SOC, HLTG, and PT, sorted in alphabetical order, the number (n) and percentage (%) of patients experiencing an adverse event. Multiple occurrences of the same event in the same patient will be counted only once in the tables within a treatment phase. The denominator for computation of percentages is the safety population.

Analysis of all treatment-emergent adverse events

The following treatment-emergent adverse event summaries will be generated for the safety population.

- Overview of treatment-emergent adverse events, summarizing number (%) of patients with any
 - Treatment-emergent adverse event
 - Treatment-emergent AESIs
 - Serious treatment-emergent adverse event
 - Treatment-emergent adverse event leading to death
 - Treatment-emergent adverse event leading to permanent treatment discontinuation
- All treatment-emergent adverse event by primary SOC, HLTG, and PT, showing number (%) of patients with at least 1 treatment-emergent adverse event sorted by the SOC internationally agreed order. The other levels (HLTG, PT) will be presented in alphabetical order

Analysis of all treatment emergent serious adverse event(s)

- All SAEs by primary SOC, HLTG, and PT, showing number (%) of patients with at least 1 treatment-emergent adverse event sorted by the SOC internationally agreed order. The other levels (HLTG, PT) will be presented in alphabetical order

Analysis of all treatment-emergent adverse event(s) leading to treatment discontinuation

- All TEAEs leading to treatment discontinuation by primary SOC, HLTG, and PT, showing number (%) of patients with at least 1 treatment-emergent adverse event sorted by the SOC internationally agreed order. The other levels (HLTG, PT) will be presented in alphabetical order

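### Does the mix of study discontinuation and treatment discontinuation leave the secondary endpoint unsound?

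*SAP*

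**What the plan says.** The secondary endpoint is worded the same way in the protocol synopsis, Protocol 9.2, SAP 2.1.4 and SAP 2.4.5: "Incidence rates for AEs leading to study discontinuation over the study". SAP 2.4.5.1 attaches the exact interval to that event: "Incidence rates with corresponding 95% CI (Clopper-Pearson method) will be presented for AEs leading to study discontinuation over the study". The protocol's analysis section also uses study discontinuation, in 11.4.3.1.1 ("TEAE leading to discontinuation of the study will be tabulated") and in the 11.4.3.1.2 overview ("Any AE leading to permanent study discontinuation").

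Three places use stopping treatment instead:

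- the key-analysis line of the synopsis: "All TEAEs, AESIs, SAEs, and AEs leading to treatment discontinuation will be summarized";
- the note under Protocol 9.2 on data collection: "AEs leading to IMP discontinuation, and death will be collected from the time of informed consent signature";
- the SAP 2.4.5.1 overview, with the row "Treatment-emergent adverse event leading to permanent treatment discontinuation", and its breakdown by system organ class, high level group term and preferred term.

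Protocol 10.3.2 defines the treatment event: "Permanent treatment discontinuation is any treatment discontinuation associated with the definitive decision from the Investigator not to re-expose the patient to the IMP". Neither document gives a matching definition of an adverse event that leads to study discontinuation.

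**The concern.** Stopping treatment and leaving the study are separate events in this design. Protocol 10.1.5 gives early stoppers a last visit 12 weeks after the end-of-treatment visit, and SAP 2.2 lists the two kinds of discontinuation as separate disposition categories. A patient who stops dupilumab because of an adverse event and attends that last visit might therefore not count in the endpoint, so the percentage carrying the endpoint label could sit below the rate of adverse-event treatment stops.

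The numerator also looks loose. Protocol 10.4.2 asks, for each adverse event, what was done with the study drug, and names no equivalent item for leaving the study. The event set varies too: 11.4.3.1.1 takes treatment-emergent events, 11.4.3.1.2 takes any adverse event, and SAP 2.4.5.1 takes events over the study. Finally, the SAP overview swaps the protocol's study-discontinuation row for a treatment-discontinuation row, while SAP 1.5 records no modification. At stake is a secondary safety endpoint that two programmers might derive differently, and an interval placed on what may be the smaller of two figures.

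**Working it through.** The documents state no expected rate for this endpoint, so there is no figure to reproduce. The check is a comparison of the texts, followed by an illustration of size.

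**Which event is the endpoint?** Every place that names the endpoint says study discontinuation: synopsis endpoints, Protocol 9.2, SAP 2.1.4, SAP 2.4.5, and the interval sentence in SAP 2.4.5.1. Protocol 11.4.3.1.1 and 11.4.3.1.2 agree. The 9.2 note concerns collection and reporting, and refers to 11.4.3.1 for analysis, where the tabulated event is study discontinuation. The treatment-stop tables in SAP 2.4.5.1 belong to the general summaries of treatment-emergent events and do not redefine the endpoint.

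**Is there a data source?** Protocol 10.3.5 requires every study withdrawal to be entered in the eCRF, with at least its date and reason in the medical record. SAP 2.2 reports study discontinuation by main reason, so the reason must reach the database. An analyst would count safety-population patients whose main reason is an adverse event. The list in 10.4.2 says what the investigator should specify for each event. It is not an inventory of eCRF fields, so it cannot show that no other link exists.

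**Does the choice of event set matter?** At the start, consent and first dose both belong to Visit 1 (Protocol 10.1.1), and patients never dosed are outside the safety population. At the end, the SAP 2.4.5 window for early stoppers runs to last dose + 84 days, and the final visit falls 12 weeks (12 × 7 = 84 days) after the end-of-treatment visit. For early stoppers the two sets should differ mainly by the interval between last dose and the end-of-treatment visit.

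**How far apart could the two percentages be?** Inputs: N = 750 (expected enrolment, Protocol 11.1 and SAP 1.3); the number of adverse-event treatment stops, x, is assumed; the share f of those patients who also count as leaving the study because of the event is assumed.

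- Endpoint = f × x / 750.
- Clopper-Pearson lower limit = 0.025 quantile of Beta(k, 750 − k + 1); upper limit = 0.975 quantile of Beta(k + 1, 750 − k), where k is the count. For k = 0 the lower limit is 0.

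| Assumed treatment stops | Treatment-stop rate (95% CI) | Endpoint if f = 1 | Endpoint if f = 0.5 | Endpoint if f = 0 |
|---|---|---|---|---|
| 30 | 30/750 = 4.00% (2.71–5.66) | 4.00% (2.71–5.66) | 15/750 = 2.00% (1.12–3.28) | 0.00% (0.00–0.49) |
| 60 | 60/750 = 8.00% (6.16–10.18) | 8.00% (6.16–10.18) | 30/750 = 4.00% (2.71–5.66) | 0.00% (0.00–0.49) |

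The f = 0 column is an arithmetic bound; nothing in the documents suggests it. Nor do they say that an early stopper who attends the last visit is not a study discontinuation. Protocol 10.3.5 gives no longer wishing to take the drug as one ground for leaving the study, and on that reading f is close to 1.

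**Is anything lost?** Under every f, the treatment-stop number and percentage appear in the SAP 2.4.5.1 tables, and treatment stops by main reason appear in SAP 2.2. An interval for the treatment-stop row follows from its count and the safety-population size by the formula above.

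**The case for a change.** The strongest case for a change is that, in a descriptive safety study, clear numerators and labels are most of the analytic content, and this is one of only three secondary endpoints. The derivation is unwritten, the protocol itself alternates between treatment-emergent and any adverse event, and the 9.2 note promises analysis of treatment stops in a section that tabulates only study discontinuation. The SAP then changes the overview row without recording it. A sentence or two and a log entry would cost almost nothing.

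The textual observations stand. The derivation and event set are not spelled out, the SAP overview does differ from Protocol 11.4.3.1.2, and the combined end-of-treatment/end-of-study label in the synopsis and Protocol 10.1.3 sits awkwardly beside 10.1.4 and 10.1.5. They do not show that the plan, followed as written, gives an unsound result. The missing derivation has a natural answer in data already planned for reporting. The unrecorded row and the visit label are clerical. An extra interval on the treatment-stop row would tell the reader nothing that its count and denominator do not. An undercount is possible, but it depends on one reading of what counts as leaving the study.

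**Conclusion.** No change to the plan follows. The endpoint is consistently adverse events leading to study discontinuation, its denominator (the safety population) and interval method are stated, and the treatment-stop counts are reported alongside it. What remains is a detail that analysts can fill sensibly, an interval that adds no information, and some clerical untidiness.

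The size of any gap between the two percentages is unknown. With an assumed 30 treatment stops in 750 patients it lies between 0 and 4.00 percentage points, but the larger figure is reported in either case. The conclusion rests on three assumptions: that the main reason for study discontinuation is held in the database, as SAP 2.2 implies; that the report labels the two quantities distinctly; and that no formal comparison depends on this endpoint, which the single-arm, noncomparative design supports.

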11.4.3.1.3 Adverse events of special interest

The incidence of each AESI and the number of AESIs per 100 patient-years will be presented; AESI definitions can be found in [Section 10.4.1.3](#).

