1.5 MODIFICATIONS TO THE STATISTICAL SECTION OF THE PROTOCOL

Not applicable

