1.6 STATISTICAL MODIFICATIONS MADE IN THE STATISTICAL ANALYSIS PLAN

Date	Modification	Reviewer
March 3, 2021	Added COVID-based analysis section (section 2.4.5.6)	[REDACTED]

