2.4.3.1 Extent of investigational medicinal product exposure

The extent of IMP exposure will be assessed by the duration of IMP exposure.

Duration of exposure to IMP is defined as: last dose date – first dose date of dupilumab + 14, regardless of unplanned intermittent discontinuations. Duration of exposure will be

Statistical Analysis Plan
LPS15023 - Dupilumab
summarized using descriptive statistics such as mean, standard deviation (SD), median, minimum, and maximum.

15-Mar-2021
Version number: 2.0

Duration of IMP exposure will be summarized descriptively as a quantitative variable (number, mean, SD, median, minimum, and maximum). In addition, duration of treatment exposure will also be summarized categorically by numbers and percentages for each of the following categories and cumulatively according to these categories in days: >0-4, >4-12, >12-24, >24-48, >48-72, >72-96, >96-120, >120-142, >142.

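### The protocol plans TEAE event rates per 100 patient-years by SOC, HLGT and PT, but the SAP states no by-term rate and records no change

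*SAP*

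**What the plan says.** Protocol 11.4.3.1.1 opens with TEAE incidence and, in the same sentence, the "number of TEAEs per 100 patient-years (total number of events adjusted for the total duration of exposure) will be presented by system organ class"; the sentence continues to HLGT and PT. Both measures are thus set at term level. For AESIs, Protocol 11.4.3.1.3 asks separately for both: "The incidence of each AESI and the number of AESIs per 100 patient-years will be presented".

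SAP 2.4.5.1 defines the TEAE event rate by one formula, TEAEs divided by person-years, with an exact Poisson confidence interval. On the numerator it says "All events reported during the study follow-up period will be counted, regardless of whether they are reported in the same subject". It carries the same method over to AESIs. It mentions no breakdown of the rate by SOC, HLGT or PT.

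For term level, the same section says "Adverse event incidence tables will present by SOC, HLTG, and PT, sorted in alphabetical order, the number (n) and percentage (%) of patients". The individual tables it lists (all TEAEs, serious events, TEAEs leading to treatment discontinuation) and the table of TEAEs leading to death in SAP 2.4.5.2 all show the number and percentage of patients.

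SAP 1.5, headed "MODIFICATIONS TO THE STATISTICAL SECTION OF THE PROTOCOL", is marked not applicable. SAP 1.6 has one entry, dated March 3, 2021, for the COVID-19 analyses. SAP 7 lists no appendices, so no table shell in the SAP supplies the missing output.

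**The concern.** The protocol names an output and the SAP, which should carry it out, does not mention it. A programmer who works only from the tables listed in SAP 2.4.5.1 and 2.4.5.2 would deliver one overall TEAE rate, the AESI rates, and counts and percentages of patients by term. The log of changes would give no hint that anything planned was missing.

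In this study the by-term rate carries information that the percentage does not. Treatment runs until approval and market availability or to a maximum of 144 weeks (SAP 1.4), so follow-up differs between patients by design. The study is single-arm and descriptive, and its stated interest is long-term safety. The term-level table is where a reader would look to see which events recur and how often they occur per unit of exposure. A percentage of patients answers neither question.

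**Working it through.** The check is mainly a comparison of texts, followed by a short illustration of what the percentage leaves open. The plan gives no figure of its own to reproduce.

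**1. The outputs side by side**

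| Output | Protocol 11.4.3.1 | SAP 2.4.5.1 and 2.4.5.2 |
|---|---|---|
| TEAE incidence by term | planned | specified |
| Overall TEAE event rate | primary endpoint (9.1.1) | specified, with exact Poisson CI |
| AESI event rate | planned | specified, with exact Poisson CI |
| TEAE event rate by SOC, HLGT, PT | planned | not stated |

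Only the last row differs.

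**2. Can the by-term rate be rebuilt from the planned tables?**

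- Denominator: approximately yes. SAP 2.4.3.1 says "Duration of IMP exposure will be summarized descriptively as a quantitative variable (number, mean, SD, median, minimum, and maximum", so mean exposure times the number of patients gives total person-time. The overall rate needs the same total.
- Numerator: no. The by-term tables give patients, and no planned by-term table gives the number of events.

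**3. What a row of the planned table leaves open**

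Inputs: N = 750 (expected enrolment, SAP 1.3) and 144 weeks (maximum treatment, SAP 1.1). Assumed, because the documents give no such figures: a PT reported by 30 patients, all patients followed for 144 weeks, and 1, 2 or 3 events in each affected patient.

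- Person-years = 750 × 144 × 7 / 365.25 = 2,069.8. This is a ceiling, since treatment can stop earlier.
- Planned row: 30 / 750 = 4.0%.
- Rate = 100 × events / 2,069.8.

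| Events per affected patient | Events | Rate per 100 patient-years |
|---|---|---|
| 1 | 30 | 1.45 |
| 2 | 60 | 2.90 |
| 3 | 90 | 4.35 |

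The same row, 30 (4.0%), fits all three. The ratio of highest to lowest is 90 / 30 = 3 whatever the person-time, because the person-years cancel.

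**4. The denominator that an added rate would inherit**

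SAP 2.4.5 counts events up to 14 days after the last dose in completers and up to 84 days in patients who stop early. The person-time in SAP 2.4.5.1 adds 14 days for everyone.

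- Completers: 14 − 14 = 0 days of mismatch.
- Early discontinuers: 84 − 14 = 70 days, or 70 / 365.25 = 0.19 patient-years. This is a maximum, because a patient who dies, withdraws consent or is lost is observed for less.
- If 10% to 30% of 750 stop early (assumed; 75 to 225 patients), the person-time left out is at most 75 × 0.1916 = 14.4 to 225 × 0.1916 = 43.1 patient-years. Against 2,069.8 that is 0.7% to 2.1%.

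**The case against.** The strongest reply is that the SAP does not list everything it intends to produce. Protocol 11.4.3.1.1 also plans TEAEs by maximum intensity and by relationship to study drug, and SAP 2.4.5.1 lists neither. Yet SAP 2.5.2 gives rules for missing severity and missing relationship in summary tables, so it takes such tables for granted. SAP 2.4.5.3 also refers back to Protocol 11.4.3.1. With SAP 1.5 marked not applicable, one can fairly hold that the protocol section stays in force and that the by-term rates will be produced. Nor is the rate formula expressly limited to the overall level. This stands, and it rules out one inference a reader might draw, that the sponsor deliberately dropped the analysis. It does not close the gap: if the protocol section governs, the SAP should say so, and if it does not, SAP 1.5 needs an entry.

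Two further inferences are tempting and are not supported. One is that the primary endpoint is compromised. Protocol 9.1.1 and SAP 2.1.4 define it without any term breakdown, and SAP 2.4.5.1 delivers both parts of it. The other is that the counting rule for the by-term tables, "Multiple occurrences of the same event in the same patient will be counted only once in the tables within a treatment phase", departs from the protocol. Protocol 11.4.3.1.1 has the same rule for incidence, apart from the reference to a treatment phase. The rule explains why event counts cannot be read from those tables, but it is not itself a discrepancy.

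**Conclusion.** The point holds as an unstated protocol-planned output. The protocol places the TEAE rate per 100 patient-years at SOC, HLGT and PT level, the SAP specifies only patient counts and percentages there, and no change is recorded. Followed as written, the SAP gives less than the protocol plans.

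The loss is one supporting breakdown in a descriptive, single-arm study. The overall TEAE rate and the AESI rates remain, and no comparison between arms is affected. The threefold range rests on the assumed 1 to 3 events per affected patient, and its true size in this cohort is unknown. The window mismatch of up to 70 days per early discontinuer follows directly from the SAP's definitions. Its total effect depends on an early-stopping share that the documents do not give, and it is small at the shares assumed here. It is a reason to choose the denominator with care when the rates are added, not evidence that they were dropped.

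**What to change.** In SAP 2.4.5.1, add two columns to the TEAE table by SOC, HLGT and PT: the number of events, counting every occurrence, and events per 100 patient-years. If the by-term rate is not wanted, record and justify that in SAP 1.5.

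Make numerator and denominator cover the same time, in one of two ways:

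- let person-time run to the end of each patient's event window, or to the end of observation if that comes first; or
- keep the on-treatment person-time and count for this rate only events up to 14 days after the last dose.

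Label the denominator in the table. The protocol describes the adjustment as one for duration of exposure, so note the chosen option in SAP 1.5.

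The cost is a few lines of SAP text, two table columns and one labelled denominator. No new data are needed, since the overall rate already requires the event records and dosing dates.
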